## 4.2 SCIENTIFIC RATIONALE FOR STUDY DESIGN

We conducted a pilot RCT, randomizing 62 dyads of hospitalized patients with GDS 5-7 ADRD and their family caregivers to the ADRD-PC program vs usual care with publicly available education material. While underpowered to show a difference in 60-day hospital transfers, we found marked differences in intermediate outcomes. Intervention dyads were more likely to have an active POLST advance directive (79% vs 30%,  $p<0.001$ ) and to make a decision to avoid future hospitalization (13% vs 0%,  $p=0.033$ ). With ADRD-PC, persons with late-stage ADRD had more palliative care domains addressed in their treatment plan (Palliative Care Domain index score 7.6 vs 2.7,  $p<0.001$ , range 0-10), and symptom management for dyspnea (77% vs 34%,  $p<0.001$ ), constipation (93% vs 25%,  $p<0.001$ ), depression (83% vs 25%,  $p<0.001$ ) and delirium (80% vs 19%,  $p<0.001$ ). Caregivers were more likely to discuss prognosis (90% vs 3%,  $p<0.001$ ) and goals of care (90% vs 25%,  $p<0.001$ ). Intervention dyads also increased use of post-discharge palliative care (21% vs 7%,  $p=0.124$ ) and hospice (25% vs 3%,  $p<0.019$ ). Results indicate the potential for ADRD-PC to improve patient and caregiver-centered outcomes, including hospital transfers.

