### 9.2 SAMPLE SIZE DETERMINATION

Based on prior ADRD research, we project 15% dropouts (death, withdrawal) equally distributed between groups; caregiver data collection is completed after deaths as in our prior ADRD

research. Total sample size for analysis of 60-day follow-up outcomes is thus n=360. All statistical tests will be 2-tailed with an overall 0.05 significance level for pre-specified analyses. Statistical power is based on a 2-sided alpha of 0.05 significant tests and using standard deviation estimates from our pilot study (**Table 3**).

Power calculations assume a “best guess” 15% dropout (death, withdrawal) rate based on prior ADRD research (n=180 per group at 60-day follow-up) and a “worst case” 25% dropout rate (n=159 per group). These rates consider 9% patient mortality and 92% caregiver retention rate in the pilot. In our pilot data, 0.52 is the lower bound of the 95% CI for the IRR comparing

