**Table 3: Power for Comparing Intervention and Control Arms Based upon the Study Design**

| Aim       | Measure                                   | Control | SD  | Difference | Power, 15% dropout | Power, 25% dropout |
|-----------|---|---------|-----|------------|--------------------|--------------------|
| 1  | 60-day hospital transfers (Poisson rate)  | 0.53    | --  | 0.25, 0.2  | 0.96, 0.82         | 0.95, 0.79         |
|           | 60-day hospital transfers (overdispersed) | 0.53    | --  | 0.25, 0.2  | 0.81, 0.60         | 0.76, 0.55         |
| 2a | PC Domain Index (0-10)                    | 2.7     | 1.7 | 5, 0.5     | >0.99, 0.80        | >0.99, 0.75        |
| 2b | 60-day hospice use (%)                    | 3%      | --  | 22%,8%     | >0.99, 0.85        | >0.99,0.80         |
| 2c | Symptom distress (SM-EOLD)                | 36.4    | 7.8 | 4, 2.3     | >0.99, 0.80        | >0.99, 0.75        |
| 2d | Transition to nursing home care (%)       | 33%     | --  | 30%,15%    | >0.99, 0.82        | >0.99, 0.78        |
| 3a | Discussion of dementia prognosis          | 3%      | --  | 87%, 8%    | >0.99, 0.85        | >0.99, 0.80        |
| 3a | Discussion of goals of care (%)           | 25%     | --  | 65%,14%    | >0.99, 0.82        | >0.99, 0.77        |
| 3b | Decision-making about hospitalization     | 0%      | --  | 13%, 4%    | >0.99, 0.78        | >0.99, 0.73        |
| 3b | Decision-making about treatments          | 6%      | --  | 47%, 9%    | >0.99, 0.80        | >0.99, 0.75        |
| 3c | Family Distress in Advanced Dementia      | 2.4     | 0.5 | 0.15, 0.1  | 0.81, 0.47         | 0.76, 0.43         |

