**Aim 3:** To compare caregiver-centered secondary outcomes between intervention and control arms: a) communication about prognosis and goals of care; b) shared decision-making; and c) caregiver distress (Family Distress in Advanced Dementia scale, Zarit Burden interview).

Analysis to Meet Aim 3: For the dichotomous outcome variables pertaining to communication (hypothesis 3a) and shared decision-making (hypothesis 3b), Pearson's chi-square test will test for differences in proportions between study arms. We will use logistic regression for the multivariable modeling. Treatment effect estimates will be reported as adjusted odds ratios. To test hypothesis 3c, we will use Student's t-test for mean difference since the outcome, Family Distress in Advanced Dementia (FDAD), is continuous. Linear mixed models as described for Aim 2.b. above will be used to test treatment effects for 30-day and 60-day outcomes jointly.

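### Table 3 plans decision-making about hospitalization at 0% in controls, but section 9.4.3 reports its effect only as an ordinary adjusted odds ratio, which has no finite estimate with zero control events

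*Combined protocol and SAP*

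**What the plan says.** Section 9.4.3 (Aim 3) groups the communication outcomes (3a) and the shared decision-making outcomes (3b). Arms are compared by Pearson's chi-square. For the adjusted analysis the plan says "We will use logistic regression for the multivariable modeling", and for the effect measure "Treatment effect estimates will be reported as adjusted odds ratios". It names no exact or penalised version, no risk difference and no rule for an empty cell.

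Table 3 in section 9.2 has two rows for 3b:

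- "Decision-making about hospitalization": control 0%, differences of 13 and 4 points, power above 0.99 and 0.78 (15% dropout), above 0.99 and 0.73 (25% dropout).
- Decision-making about treatments: control 6%, differences of 47 and 9 points.

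The 0% is the pilot value. Section 4.2 reports 13% versus 0% for a decision to avoid future hospitalization, in a pilot that randomized 62 dyads. Section 9.2 gives the planned size as "n=180 per group at 60-day follow-up", or 159 per group under the worst-case dropout.

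**The concern.** A planning value of 0% in one arm and an ordinary odds ratio do not go together. When no control patient has the event, the likelihood keeps rising as the log odds ratio grows, so there is no maximum. Software then stops at an arbitrary large value with a very large standard error. Adjusting for site, GDS stage or sex does not cure this, because the arm term alone still separates events from non-events in the control arm.

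At stake is the reporting of one prespecified secondary outcome. If the control arm turned out as planned, the only effect measure the plan names could not be given, and a replacement would be chosen after the data were seen. A reader comparing the chi-square p-value with the Wald p-value from the model would find them contradicting each other. The rule in section 9.4.1 that keeps or drops covariates by the change in the intervention coefficient would also have no finite coefficient to work on.

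**Working it through.** **Inputs.** Control rate 0% and difference 4 points (Table 3); 180 or 159 per arm, 1:1 allocation, two-sided alpha 0.05 (sections 4.1 and 9.2); Pearson's chi-square, logistic regression and adjusted odds ratio (section 9.4.3). The true control rate in the trial is not known and is varied below as an assumption.

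**1. The plan's own power figure.** The usual pooled formula is power = Φ[(d − 1.96·SE0)/SE1], with SE0 = √(2·p̄(1−p̄)/n) and SE1 = √((p0(1−p0) + p1(1−p1))/n).

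- n=180: p̄ = 0.02, SE0 = √(0.0392/180) = 0.01476, SE1 = √(0.0384/180) = 0.01461. Power = Φ[(0.04 − 0.02892)/0.01461] = Φ(0.758) = 0.776. Stated: 0.78.
- n=159: SE0 = 0.01570, SE1 = 0.01554. Power = Φ[(0.04 − 0.03078)/0.01554] = Φ(0.594) = 0.724. Stated: 0.73.

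The figure reproduces.

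**2. The odds ratio at the planned values.** At 4% of 180 the expected intervention count is 7.2; take 7. The table is 0/180 versus 7/180.

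- Odds ratio = (7 × 180)/(173 × 0), which is infinite.
- Ordinary logistic fit: log odds ratio 8.4 (SE 14.7) after 10 iterations and 23.4 (SE about 26,500) after 25. The estimate rises by (23.4 − 8.4)/15 = 1 per iteration and does not settle. At 25 iterations z = 23.4/26,500 = 0.0009, so the Wald p is near 1. The exact SE depends on where the software stops.
- Pearson's chi-square: pooled proportion 7/360 = 0.0194, SE = √(2 × 0.0194 × 0.9806/180) = 0.01455, z = (7/180)/0.01455 = 2.67, p = 0.0075.

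The larger planned difference does not help. At 13% about 0.13 × 180 = 23 intervention events are expected, but with no control events the odds ratio is still infinite.

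**3. How likely an empty control arm is.** P(no control events) = (1 − p)^n.

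| True control rate (assumed) | n=180 | n=159 |
|---|---|---|
| 0% | 1.00 | 1.00 |
| 0.1% | 0.84 | 0.85 |
| 0.5% | 0.41 | 0.45 |
| 1% | 0.16 | 0.20 |
| 2% | 0.03 | 0.04 |

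**4. Whether a remedy gives a usable number.** In the unadjusted two-by-two table, Firth's penalty amounts to adding 0.5 to each cell: (7.5 × 180.5)/(173.5 × 0.5) = 15.6, which is finite. The risk difference is 7/180 = 3.9 points and needs no correction.

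**The case against.** The best reply is that 0% is a small-pilot result and not a forecast. If about 31 of the 62 pilot dyads were controls (an assumption), 0/31 has an exact 95% upper limit of 1 − 0.025^(1/31) = 11%. At a true rate of 2% an empty control arm is unlikely (3%). The trial measure is also worded more broadly than the pilot finding, so its control rate may well be above zero. All of this stands. It makes the failure conditional, but 0% is still the value the plan chose.

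It is also fair to say that section 9.4.3 names no Wald test or interval for Aim 3. The Wald test is specified for the primary outcome in section 9.4.2. However, a profile-likelihood interval from the same ordinary fit would have no upper limit, so the gap remains.

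Three stronger readings are tempting, and the documents do not support them.

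- *The stated power does not fit the named test.* It does: the pooled chi-square formula gives 0.776 and 0.724, and it also reproduces the rows at control rates of 3%, 25% and 6%. With about 3.6 expected events per arm the approximation is rough, but for Pearson's chi-square it is conservative, since exact enumeration gives 0.93 and 0.88. The lower exact figures for Fisher's test (0.73 and 0.61) belong to a test the plan does not name. Table 3 needs no restatement.
- *The adjusted model would break down in most trials because site, GDS or sex cells are empty.* An empty covariate cell sends that covariate's coefficient to infinity but normally leaves the arm odds ratio finite. Putting a rate on it would need covariate splits that the documents do not give, and section 9.4.3 lists no covariates for the 3a and 3b models.
- *The outcome is left without an analysis.* The chi-square test copes with an empty cell, and section 9.4.1 has frequencies and percentages reported.

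**Conclusion.** The concern holds in a narrow form. At the plan's own control rate for decision-making about hospitalization, the only effect measure named in section 9.4.3 has no finite estimate, and no alternative is prespecified. The size depends on an unknown control rate: at 180 per arm the chance of losing the odds ratio through an empty control arm runs from 100% at 0%, through 41% at 0.5% and 16% at 1%, to 3% at 2%.

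The other 3b measure, planned at 6% in controls, is not affected, nor is the primary outcome. Because the hypothesis test survives and only the adjusted estimate for one secondary measure is at risk, this is a minor point.

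**What to change.** Add one rule to section 9.4.3, for example: *For a dichotomous outcome with fewer than 5 events in either arm, the adjusted odds ratio will be estimated by Firth-penalised logistic regression with profile-likelihood intervals, and the unadjusted risk difference will be reported with an exact or score interval. Pearson's chi-square remains the test.*

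The threshold of 5 is an example; what matters is that it is fixed before the data are seen. The cost is a sentence and standard software. The downside is a slightly less familiar estimator for what is likely to be one secondary measure.

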### Administrative Supplement Analysis:

**Supplement Aim 2: To determine the feasibility, acceptability and preliminary efficacy of the ADRD-PC intervention for n= 50 Hispanic / Latino dyads living with late-stage dementia in a pilot randomized clinical trial:** Descriptive analyses of variables will examine distributions, influential data points, and missing data. Means (standard deviations) will be reported for continuous variables and frequencies with percentages for categorical variables. Continuous variables (e.g., PC Domain Index, etc) that are poorly distributed may be transformed, or analyzed using non-parametric tests. We anticipate that missing data on independent variables will be minimal. We will use simple mean and mode imputation for those variables included in regression models if less than 5% of patients have missing data; else, conditional (i.e., regression) imputation will be used. Available case analyses will be conducted for 30-day outcomes. Missing 60-day dichotomous outcomes will be multiply imputed if

missingness exceeds 10%. Caregiver data collection is completed after deaths as in our prior ADRD research.

**Analysis of feasibility outcomes:** Simple descriptive statistics will be used to assess feasibility. We will report frequencies for rates of screening, eligible vs. ineligible, and consented vs. refused dyads. We will report on de-identified demographic and clinical characteristics of those who are eligible and consent vs refuse participation. We will use similar descriptive comparisons to report on dyads who enroll and complete all study procedures compared to those who are not retained for complete outcome assessments. ADRD-PC will be feasible for Hispanic / Latino dyads if we successfully achieve target enrollment (n=50 dyads), and study retention (80%) within 20% these goals.

**Analysis of acceptability outcomes:** Acceptability will be evaluated using qualitative methods to analyze results of open-ended questions in family caregiver interviews. Interview transcripts will be entered into ATLAS.ti software to facilitate qualitative content analysis and coding. [name] will oversee the qualitative coding process, and two Spanish-speaking CRCs will conduct paired coding of all transcripts.

**Analysis of preliminary efficacy outcomes data:** Primary analysis will use intention-to-treat analysis. We will evaluate the effectiveness of randomization by comparing intervention and control participants on baseline measures. Variables that are not equally distributed between arms could potentially bias results. We will include these variables in each initial model and use a change-in-effect method for determining whether they are confounders. If removing any of these variables from the model does not appreciably change the regression coefficient estimate associated with the intervention group variable, we will not need to include them in the final model. Given our randomized design, we anticipate little confounding. A priori exploratory analyses will examine the effects stratified by sex as a biologic variable, and GDS stage.

As in the parent ADRD-PC randomized trial, we will compare control and intervention arms on hospital transfers (primary outcome) during 60 days post-discharge. This count outcome is defined as total number of emergency room visits plus hospital admissions per at-risk patient-days. We will use Poisson regression with empirical 'robust' standard errors allowing for overdispersion to compare the transfer rates between groups. We will use length of follow-up as the offset variable, which means that patients who have data only from the 30-day interview will be included. The primary analysis will be based on the model with main effects for treatment group, study site, GDS Stage and patient and caregiver sex as biological variables. Evaluation of the treatment effect will be based on a Wald test. The covariate-adjusted treatment effect will be quantified as an incidence rate ratio (IRR) with 95% confidence interval. We will conduct a sensitivity analysis for the treatment effect on 60-day hospital transfers with a marginalized zero-inflated Poisson (MZIP) model, that may modestly increase power. Secondary Poisson and MZIP analyses will compare study arms for 30-day hospital transfer rates. An exploratory analysis will be conducted to examine interactions of treatment group with study site, sex and GDS Stage, respectively, on 60-day hospital transfers. An interaction model will be used if an omnibus test for interactions is statistically significant at the 0.05 level.

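### The 50-dyad Hispanic/Latino pilot reuses the parent trial's robust Poisson Wald test with no small-sample correction; with the uncorrected variance and a normal reference, a nominal 5% test would reject a true null about 7–12% of the time

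*Combined protocol and SAP*

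**What the plan says.** Section 9.4.3, under Administrative Supplement Analysis, makes it an aim to assess "preliminary efficacy of the ADRD-PC intervention for n= 50 Hispanic / Latino dyads" in a pilot randomized trial. Its efficacy paragraph takes over the parent trial's primary analysis from Section 9.4.2: "As in the parent ADRD-PC randomized trial, we will compare control and intervention arms on hospital transfers". The method is "We will use Poisson regression with empirical 'robust' standard errors allowing for overdispersion", with follow-up length as offset. The covariates are fixed by "The primary analysis will be based on the model with main effects for treatment group, study site, GDS Stage and patient and caregiver sex", and the inference by "Evaluation of the treatment effect will be based on a Wald test". The result is to be reported as an adjusted incidence rate ratio (IRR) with a 95% interval.

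Neither Section 9.4.2 nor Section 9.4.3 says which form of the robust variance is meant, whether the Wald statistic is referred to a normal or a t distribution, or on how many degrees of freedom. Section 9.2 sets two-sided testing at 0.05.

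**The concern.** Robust standard errors rest on a large-sample argument. The sandwich uses squared residuals, and fitted residuals are too small on average when the model has many coefficients for the number of patients. A method that is harmless at 360 dyads need not be so at 50.

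What is at stake is the honesty of the interval. The supplement's power statement in Section 9.2 warns readers to expect little power, which means a wide interval. It does not warn them that an interval labelled 95% may cover less than that.

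**Working it through.** **Inputs from the documents**
- n = 50, allocated 1:1 (Sections 9.4.3 and 4.1).
- Five sites (Section 4.1) and GDS 5, 6 or 7 (Section 5.1).
- Control rate 0.53 transfers per 60 days, differences 0.25 and 0.2 (Section 9.2, Table 3).

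**Size of the model.** With site and GDS categorical, p = 1 (intercept) + 1 (arm) + 4 (site) + 2 (GDS) + 2 (sex terms) = 10. With 2 sites and 2 GDS levels, p = 6. Expected events with no effect: 50 × 0.53 = 26.5, or 2.65 per coefficient at p = 10. With a difference of 0.25: 25 × 0.53 + 25 × 0.28 = 20.25.

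**Overdispersion implied by Table 3.** Power = Φ(d / √(φ(λ0+λ1)/n) − 1.96), with n per arm.
- φ = 1, d = 0.25, n = 180: 0.25/√(0.81/180) = 3.727, so power is Φ(1.767) = 0.961 (stated 0.96). The other three Poisson entries come out at 0.825, 0.939 and 0.776 (stated 0.82, 0.95, 0.79).
- φ = 1.7 gives 0.815 and 0.602 at 15% dropout, and 0.766 and 0.550 at 25% (stated 0.81, 0.60, 0.76, 0.55).

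All eight entries agree within 2 points, so a variance-to-mean ratio of about 1.7 is the plan's own level.

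**Variance forms.** V = A⁻¹ [Σ kᵢ (yᵢ−μᵢ)² xᵢxᵢ′] A⁻¹, with A = Σ μᵢxᵢxᵢ′. HC0 has kᵢ = 1, HC1 has kᵢ = n/(n−p), and HC2 has kᵢ = 1/(1−hᵢ), where hᵢ is the leverage.

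**Rough hand check.** Mean leverage is p/n, so HC0 understates the standard error by a factor of about √(1−p/n), and a true null is rejected with probability about 2[1−Φ(1.96√(1−p/n))].
- n = 50, p = 10: 1.96√0.80 = 1.753, giving 8.0%.
- n = 50, p = 6: 1.96√0.88 = 1.839, giving 6.6%.
- n = 360, p = 10: 1.96√0.972 = 1.933, giving 5.3%.

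**Simulation.** Gamma-Poisson counts, mean 0.53 in both arms and all GDS stages; planned main effects and offset; 24,000 null trials per row. Entries are % rejection at nominal 5%, without / with variance-to-mean ratio 1.7.

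| Setting (n = 50) | p | HC0, normal | HC1, normal | HC2, normal | HC2, t(n−p) |
|---|---|---|---|---|---|
| 5 sites, 3 GDS levels | 10 | 8.9 / 11.3 | 5.8 / 7.6 | 5.3 / 6.4 | 4.6 / 5.6 |
| 3 sites, 3 GDS levels | 8 | 7.9 / 10.1 | 5.5 / 7.2 | 5.3 / 6.5 | 4.7 / 5.7 |
| 2 sites, 2 GDS levels | 6 | 6.9 / 8.4 | 5.3 / 6.7 | 5.2 / 6.4 | 4.6 / 5.7 |

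Separately coded runs gave HC0 with a normal reference 8.7–8.8 / 11.3–11.6 (5 sites) and 6.7–7.4 / 8.1–9.0 (2 sites).

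**Sensitivity (5 sites, HC0 with a normal reference)**
- 20% of patients with half follow-up: 9.2 / 12.0.
- Uneven sites (20/12/8/6/4): 9.0 / 10.6.
- 40 dyads analysed (80% of 50): 10.6 / 12.7 in one set of runs, 10.8–14.8 across dispersion levels in another.
- GDS 7 rate near zero, overall mean still 0.53: 10.8 / 13.0 and 11.0 / 14.2 in two sets of runs. Here HC1 with a normal reference reaches up to about 10, while HC2 with t gives 5.1–6.3.
- Parent size, n = 360: 5.2–5.4 in one set; 6.0 in a smaller overdispersed run, where every corrected form gave 5.7.

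**Coverage at IRR 0.53 (0.28/0.53), HC0 with a normal reference:** 91.3 / 90.0 (5 sites), 92.0 / 91.4 (3) and 94.0 / 91.9 (2). A separate run gave 87.7 for 5 sites with overdispersion. HC2 with t gave 94.8–96.4, and 94.3 in that separate run.

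**The case against.** The plan never says it will use the uncorrected variance with a normal reference. An analyst who takes HC1 or HC2 already gets about 5–8% under equal GDS rates. This stands: the defect is conditional on an unstated choice. But the wording used most naturally means the uncorrected form, and the choice moves the error rate from about 5% to about 11%, so it should not be left open.

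The supplement is openly a pilot. Section 9.2 disclaims power, and the success rule is "target enrollment (n=50 dyads), and study retention (80%) within 20% these goals". This also stands, and it is why the priority is low. It does not answer the coverage point.

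The exact percentages depend on assumptions. Section 4.1 does not say how many sites enrol the 50 dyads, and equal rates across GDS stages sit badly with Section 4.3, where no GDS 7 patient in the team's pilot trial had a 60-day transfer. Hence the ranges. Removing GDS 7 events makes the uncorrected test worse, not better. The 40-dyad case is pessimistic, since "patients who have data only from the 30-day interview will be included" and the record review in Section 8.1 may keep n nearer 50.

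The plan also enters imbalanced baseline variables and drops them by change in effect. That step was not simulated, so the performance of the corrected test under the full procedure is untested.

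**Conclusion.** The point holds conditionally. With the uncorrected sandwich and a normal reference, the 50-dyad test rejects a true null about 7–12% of the time, given equal GDS rates and overdispersion up to the Table 3 level. With almost no GDS 7 events the range is about 11–14%, and with about 40 dyads analysed about 11–15%. Coverage at IRR 0.53 is about 88–94%. Site count, site split, covariate mix and GDS-specific rates are assumptions.

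A reader might infer three stronger things that the documents do not support. One is that the reported interval will certainly under-cover: the plan does not name the variance form, and HC1 or HC2 would remove much of the problem. The second is that the parent trial's primary analysis shares the fault: at 360 dyads, correction changes almost nothing. The third is that a false positive would trigger a decision: feasibility is judged on enrolment and retention, not on this p-value. The harm is limited to a possibly misstated interval in the pilot report. Low priority, worth considering.

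**What to change.** Add one sentence to the efficacy paragraph of the Administrative Supplement Analysis in Section 9.4.3, for the 50-dyad analysis only: keep the planned covariates and offset, and base both the Wald test and the 95% interval on the HC2 robust variance with a t reference on n−p degrees of freedom, p being the number of coefficients in the fitted model. Simulated rejection at n = 50 is then about 4.5–6.3% (down to 4.0% in one smaller set of runs).

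The cost is wording plus a wider log-scale interval: about 18–20% wider than the uncorrected form at 10 coefficients, and 10–11% at 6. As a yardstick, the simpler HC1 scaling with t at p = 10 gives √(50/40) × 2.021/1.96 = 1.15. Comparability with the parent model is kept, and the parent analysis needs no change.
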